#### **12.1.2. Monitoring of the Study**

The clinical monitor, as a representative of Alector, has the obligation to follow the study closely. In doing so, the monitor will visit the Investigator and study site at periodic intervals, in addition to maintaining necessary telephone and letter contact. The monitor will maintain current personal knowledge of the study through observation, review of study records and source documentation, and discussion of the conduct of the study with the Investigator and personnel. In addition, under the exceptional circumstances of the COVID-19 pandemic, the monitor may follow the study closely through remote monitoring and/or remote conduct of Investigator and study site visits, as allowed per local regulations. Refer to [Section 14.4](#) for additional details on remote source document verification as a result of the COVID-19 pandemic.

All aspects of the study will be carefully monitored by Alector or its designee for compliance with applicable government regulation with respect to current GCP and current SOPs.

### **12.1.3. Inspection of Records**

Investigators and institutions involved in the study will permit study-related monitoring, audits, IRB/IEC review, and regulatory inspections by providing direct access to all study records. In the event of an audit, the Investigator agrees to allow Alector, representatives of Alector, and/or a regulatory agency access to all study records.

The Investigator should promptly notify Alector and the CRO of any audits scheduled by any regulatory authorities. Dependent upon the scope of the regulatory authority audit, Alector may elect to assist the site in preparation or support. The Investigator should promptly forward copies of any audit reports received to Alector.

## **12.2. Study Termination**

Although Alector has every intention of completing the study, Alector reserves the right to discontinue the study at any time for clinical or administrative reasons.

The end of the study is defined as the date on which the last participant completes the last visit (including the EOS/ET Visit).

## **12.3. Final Report**

Whether the study is completed or prematurely terminated, Alector will ensure that the CSR is prepared and provided to the regulatory agency(ies) as required by the applicable regulatory requirement(s). The Sponsor will also ensure that the CSR in marketing applications meets the standards of the ICH Harmonised Tripartite Guideline E3: Structure and Content of Clinical Study Reports.

Where required by applicable regulatory requirements, an Investigator signatory will be identified for the approval of the CSR. The Investigator will be provided reasonable access to statistical tables, figures, and relevant reports and will have the opportunity to review the complete study results.

Upon completion of the CSR, Alector will provide the Investigator with the full summary of the study results. The Investigator is encouraged to share the summary results with the study participants, as appropriate. The study results will be posted on publicly available clinical trial registers.

## 14. APPENDICES

### 14.1. Appendix 1: Schedule of Assessments

**Table 9: Schedule of Assessments**

Study Week a	█	█	█	█	█	█	█	█	█	█	█	█	█	█	█	█
Visit Window		±5d														
Informed consent	x															
Social history b	x															
Demographic data	x															
Viral serology c, e	x															
Height and weight f	x	x	x	x	x	x	x	x	x	x	x	x	x	x	x	x
Vital signs c, h, i	x	x	x	x	x	x	x	x	x	x	x	x	x	x	x	x
Complete PE k	x														x	x
Limited PE c, m					x				x							
Neurological examination l	x			x		x		x		x		x		x	x	x
Ophthalmological examination c, d	x					x				x				x	x	x
Concomitant medications n	x	x	x	x	x	x	x	x	x	x	x	x	x	x	x	x
Study drug administration		x	x	x	x	x	x	x	x	x	x	x	x	x		
Adverse events c, i, o	x	x	x	x	x	x	x	x	x	x	x	x	x	x	x	x
ECG (single) c, p	x	x	x		x			x						x	x	x
Pregnancy test (if applicable) j	x													x	x	x
Thyroid function c	x															

**Table 9: Schedule of Assessments (Continued)**

Study Week a															
Visit Window		±5d													
Folic acid and vitamin B12 levels c	x														
Hematology and chemistry c, q, r	x	x			x				x					x	x
Coagulation c, s	x													x	x
Urinalysis c, t	x	x							x					x	x
C-SSRS c															
MRI (safety, PD) c, g, u															
CDR c, v, z															
MMSE c, v, z															
ADAS-Cog13 c, v, z															
RBANS-Update c, v, z															
ADCS-ADL-MCI c, v, z															
Serum PK sample(s) i															
Serum sample for ADA c, w															
Plasma sample for biomarkers c															
LP for CSF (optional) c, y, z, aa, cc															
Tau PET (optional) c, x, bb, cc, dd															
Longitudinal Amyloid PET (optional) c, x, cc, dd															

[F]MK-6240=fluorine-18 MK-6240; ADA=anti-drug antibody (-ies); ADAS-Cog13=Alzheimer’s Disease Assessment Scale-Cognitive Subscale; ADCS-ADL-MCI=Alzheimer’s Disease Cooperative Study-Activities of Daily Living – Mild Cognitive Impairment Scale; AE=adverse event; AESI=adverse event of special interest; ARIA=amyloid-related imaging abnormality; BMW=Brain MRI Worksheet; BP=blood pressure; C-SSRS=Columbia-Suicide Severity Rating Scale; CDR®=Clinical Dementia Rating; COA=clinical outcome assessments; CSF=cerebrospinal fluid; d or D=day; ECG=electrocardiogram; eCRF=electronic case report form; EOS=End of Study; ET=early termination; ICF=informed consent form; LP=lumbar puncture; MMSE=Mini-Mental State Examination; MRI=magnetic resonance imaging; PD=pharmacodynamic(s); PE=physical examination; PET=positron emission tomography; PK=pharmacokinetic(s); RBANS-Update=Repeatable Battery for the Assessment of Neuropsychological Status-Update; RNA=ribonucleic acid; SCR=screening (ie, initial study visit); SAE=serious adverse event; WOCBP=woman of childbearing potential.

- a. Study Day number and Study Week number begin with 1 on the day of the first administration of study drug.
- b. Only new events or changes in the participant's social history prior to the initial dosing on Day 1/Week 1 are to be reported in the relevant social history section of the participant's eCRF.
- c. The screening/baseline period will begin on or at the final dosing visit of the parent study AL002-2 and upon signing of the ICF. This period will be used to schedule and perform required safety and/or efficacy assessments not captured during the final dosing visit in the parent study AL002-2. It can also be utilized to schedule and perform optional biomarker assessments prior to dosing on Day 1/Week 1. If the COAs or LP were collected in the last 12 weeks prior to Day 1/Week 1 or if the PET scans were done in the last 24 weeks prior to Day 1/Week 1, these will not have to be collected during the screening/baseline period. If the COAs or LP were collected in the 12 weeks preceding the ET Visit, these will not have to be collected at the ET Visit. If the PET scans were done in the 24 weeks preceding the ET Visit, these will not have to be collected at the ET Visit. The C-SSRS must always be collected during the screening/baseline period and at the ET Visit regardless of the last collection date. If an ophthalmological examination was performed within the last 8 weeks, it will not be required at EOS/ET.
- d. Ophthalmologic examinations have a window of  $\pm 14$  days (longer than the standard visit window). See [Section 7.12](#) for additional examinations required for findings suggestive of ████████.
- e. Viral serology panel includes: human immunodeficiency virus (-1 or -2 antibody and antigen), hepatitis B surface antigen, hepatitis B surface antibody, total hepatitis B core antibody, and hepatitis C antibody/RNA. Participants with a positive hepatitis C virus antibody will be allowed if hepatitis C RNA is negative.
- f. Height and weight will be measured at screening/baseline; weight will also be measured at all other indicated timepoints.
- g. Perform/collect prior to dosing. For all post-screening MRIs, the MRI should occur at least 5 days prior to the next dose administration and no more than 10 days prior to the next dose administration, with results received from the central imaging vendor prior to dosing. Note that the central imaging vendor typically requires 5 business days after receipt of the MRI before sending a BMW to the site. MRIs may be scheduled outside of the prescribed window, with approval from the Medical Monitor. The Sponsor may request that additional unscheduled MRIs be performed for the detection and follow-up of ARIA. Participants with MRI evidence of ARIA should be managed according to instructions provided in [Table 8](#).
- h. Vital signs include temperature, respiratory rate, pulse rate, and systolic and diastolic BP while the participant is at rest in a supine position for at least 3 minutes. Heart rate and BP measurements should be obtained with a validated digital monitoring device where available and an appropriately sized cuff. The same arm should be used for all BP measurements if possible. Heart rate and BP should not be measured unless 15 minutes have passed since the last blood draw.
- i. Perform/collect prior to dosing, and at the end of the infusion. Vital signs will be collected and concomitant medications and AEs documented prior to and at the end of infusion. On dosing visits, serum PK samples will be collected pre-dose. On non-dosing visits, serum PK samples may be collected at any time during the visit. Blood samples for assessment of ADA will be taken throughout the study.
- j. Urine pregnancy test (WOCBP only) and vital signs will be performed, and concomitant medications and AEs will start being collected at the screening/baseline visit and subsequent visits for those participants participating in a Tau PET scan.
- k. Complete PE includes evaluation of the head, eyes, ears, nose, and throat, and the cardiovascular, dermatological, musculoskeletal, respiratory, and gastrointestinal systems. Breast, rectal, and genitourinary exams should be performed as clinically indicated. Limited exams should include cardiovascular, respiratory, and gastrointestinal systems. Symptom-directed PEs may also include any other pertinent system as required.
- l. Neurological examination includes an evaluation of consciousness, orientation, cranial nerves, motor and sensory system, coordination and gait, and reflexes.
- m. Perform a limited, symptom-directed PE at specified timepoints or as clinically indicated.
- n. Includes any medication (eg, prescription drugs, herbal or homeopathic products, vitamins, minerals, vaccines, topical medications, and over-the-counter medications) used by a participant from 14 days prior to initiation of study drug to the final study visit.

- o. AEs, AESIs, and SAEs will be assessed after the participant signs the informed consent until the EOS participation. Any unresolved AEs, AESIs, and SAEs will be followed up through resolution or return to baseline. Additionally, SAEs considered related to study drug or [F]MK-6240 radiotracer, which occur at any time during the study, will be reported until resolution, participant withdrawal of consent, loss to follow-up, or death, whichever is applicable. Definitions describing what is and is not considered an AE are provided in [Section 7](#).
- p. A single 12-lead ECG will be obtained before blood draws (pre-dose) on appropriate days. A single 12-lead ECG will be performed pre-dose and 60 to 90 minutes after the end of infusion on Day 1/Week 1, Weeks 5, 13, 25, and 49. The ECG must be performed after the participant has been resting (supine) for 10 minutes.
- q. Hematology includes hemoglobin, hematocrit, mean corpuscular hemoglobin, mean corpuscular volume, mean corpuscular hemoglobin concentration, white blood cells, red blood cells, platelet count, and differential count (neutrophils, lymphocytes, monocytes, basophils, eosinophils, and other cells).
- r. Chemistry panel (serum or plasma) includes sodium, potassium, chloride, calcium, glucose, bicarbonate, albumin, total protein, creatinine, hemoglobin A1c, blood urea nitrogen or urea, aspartate aminotransferase, alanine aminotransferase, gamma glutamyl transpeptidase, alkaline phosphatase, phosphorus, total bilirubin (direct and indirect), amylase, cholesterol (total, low-density lipoprotein, high density lipoprotein), triglycerides, uric acid, creatine phosphokinase, lactate dehydrogenase, magnesium, and C-reactive protein.
- s. Coagulation panel includes prothrombin time with international normalized ratio, activated partial thromboplastin time. If the LP is required for the EOS, the coagulation panel will be performed at the visit immediately preceding the EOS Visit within 4 weeks ±5 days.
- t. Urinalysis: Dipstick (pH, specific gravity, glucose, protein, ketones, blood). Microscopic analysis in the event of abnormal dipstick results (urinary sediment, red blood cells, white blood cells, casts, crystals, epithelial cells, bacteria).
- u. Screening/baseline MRI is to occur as close to the beginning (Day -28) of the window as possible and at least 10 days prior to enrollment, for those who have not had a brain MRI in the 90 days preceding the first dose on Day 1/Week 1.
- v. Perform COAs prior to any potentially stressful procedure (eg, LPs, imaging).
- w. Additional ADA samples should be collected in participants with signs and symptoms of infusion-related reactions. A corresponding additional PK sample should be obtained at the same timepoint.
- x. Informed consent and confirmation of eligibility must be received prior to performing PET scans.
- y. Participants who discontinue due to ARIA may be requested to have an LP per Investigator discretion.
- z. Per footnote v, COAs should be performed prior to LP. If possible, LP should not be performed on the same day when COAs are performed. Participants will be required to stay in the clinic or hospital for a minimum of 30 minutes after the procedure. LPs performed during the screening/baseline period will be performed at least 5 days prior to the expected Day 1/Week 1 dosing visit. LP should not be performed unless results from coagulation laboratory assessments were within clinically acceptable limits within 4 weeks ±5 days.
- aa. If an ET Visit is initiated, the final optional CSF sampling should be performed at that visit. If an ET is not initiated, optional CSF sampling should be performed at [REDACTED].
- bb. For participants in countries where local regulations allow, baseline (optional) Tau PET imaging should be performed prior to dosing on Day 1/Week 1 unless obtained within 24 weeks before Day 1/Week 1 in study AL002-2. In some cases, the initial (baseline) Tau PET scan may be performed after dosing with study drug has commenced. Sponsor agreement will be needed for baseline Tau PET scans occurring after dosing has commenced. Participants who receive an optional Tau PET scan at baseline will receive 1 or more repeated scans after beginning study drug. PET imaging has a window of ±28 days (longer than the standard visit window).
- cc. If an LP and an MRI are performed in the same visit, either (a) the MRI should be performed first or (b) the MRI should be performed at least 3 days after the LP. This minimizes the effect of CSF removal on brain volume measurements. If an LP and a PET scan are performed in the same visit, either (a) the LP

should be performed first or (b) the LP should be performed at least 12 hours after the PET scan. Participants who undergo both Tau PET and Amyloid PET exams at a given study visit must receive these exams on different calendar days.

dd. New longitudinal Amyloid and Tau PET imaging are required as the baseline scan for longitudinal Amyloid and Tau PET imaging if the participant opts in to the optional procedures unless already obtained within 24 weeks before Day 1/Week 1 in study AL002-2. PET imaging has a window of  $\pm 28$  days (longer than the standard visit window). Tau PET scans or Amyloid PET scans should not be performed if local restrictions for radiation exposure would be exceeded; if applicable, the site should contact the Sponsor to discuss alternative timing of Tau PET or Amyloid PET scans.

## **14.2. Appendix 2: Clinical Outcome Assessments – Neurocognitive and Functional Tests**

### **14.2.1. Clinical Dementia Rating**

Washington University's CDR® is a global assessment instrument that yields a global score, which is weighted toward memory (eg, Global CDR® Score). The sum of boxes (ie, CDR®-SB) score is a quantitative general index that provides more precision than the Global CDR® Score in participants with mild dementia (O'Bryant 2010). The CDR® characterizes 6 domains of cognitive and functional performance applicable to AD and related dementias: Memory, Orientation, Judgment and Problem Solving, Community Affairs, Home and Hobbies, and Personal Care. The necessary information to make each rating is obtained through a semi-structured interview of the participant and a reliable informant or collateral source (the study partner). Details of the CDR®, including the algorithm used to compute the Global CDR® Score, can be found at the [Knight Alzheimer Disease Research Center's website](#).

### **14.2.2. Mini-Mental Status Examination**

The MMSE (Folstein 1975) is a brief test used to screen for cognitive impairment. It is routinely used for estimating the severity of cognitive impairment and tracking cognitive changes in an individual over time. The MMSE assesses orientation (time and place), registration, attention and calculation, recent memory, language (naming, comprehension, and repetition), and constructional praxis (copying a figure). The maximum total score is 30, with a higher score indicating better cognitive performance.

### **14.2.3. Repeatable Battery for the Assessment of Neuropsychological Status**

The RBANS for this study uses the updated version and is referred to as the RBANS-Update (Randolph 2013); it is a collection of 12 subtests representing 5 neurocognitive domains: Immediate Memory, Visuospatial/Constructional, Language, Attention, and Delayed Memory. The raw scores from each subtest within a domain are converted to a summary score, or Index Score, for the domain by consulting normative data tables. The RBANS-Update also provides an overall Index Score that summarizes the participant's overall level of performance on this measure.

### **14.2.4. Alzheimer's Disease Assessment Scale-Cognitive Subscale**

The ADAS-Cog is one of the most frequently used tests to measure cognition in clinical trials for AD. The ADAS-Cog13 is a 13-item version of the test that assesses immediate and delayed memory, confrontational naming, ability to follow commands, ideational and constructional praxis, orientation, language, and attention.

### **14.2.5. Alzheimer's Disease Cooperative Study-Activities of Daily Living – Mild Cognitive Impairment Scale**

The ADCS-ADL-MCI assesses the competence of participants with AD in basic, instrumental, and complex activities of daily living; this scale is administered to the study partner.

### 14.2.6. Alzheimer’s Disease Composite Score (ADCOMS)

The ADCOMS (Wang 2016) is a composite measure comprising 4 items from the ADAS-Cog13, 2 items from the MMSE, and the 6 individual domain scores from CDR® (Wang 2016). The ADCOMS has shown improved sensitivity to clinical decline in the early AD dementia populations. The ADCOMS score will be derived from the scores on other COAs described in this section; there is no separate scale to administer to participants or study partners. Details of the ADCOMS have been published (Wang 2016).

### 14.3. Appendix 3: Management of Infusion-Related Reactions

Monoclonal antibodies such as AL002 may be associated with the potential risk for infusion-related reactions. Acute infusion-related reactions typically occur within 24 hours of infusion and may manifest as erythema, pruritis, fever, or chills and progress to an anaphylactic-type reaction. Clinical sites should be prepared to manage any acute hypersensitivity or hypersensitivity-like events. All participants will be monitored for infusion reactions or injection reactions during the infusion/injection and immediately afterwards.

Table 10 provides guidelines on management of acute infusion reactions as well as management of subsequent dosing instructions.

**Table 10: Guidelines for Management of Acute Infusion-related Reactions**

CTCAE Toxicity Grade	Treatment	Premedication at Subsequent Dosing
Grade 1 Mild transient reaction; infusion interruption not indicated; intervention not indicated	Stop infusion and monitor symptoms. If symptoms resolve without intervention, the infusion may be restarted at 50% of the original infusion rate.	None
Grade 2 Therapy or infusion interruption indicated but responds promptly to symptomatic treatment (eg, antihistamines, NSAIDs, narcotics, IV fluids); prophylactic medications indicated for ≤24 hours	
Stop infusion and monitor symptoms. Additional appropriate medical therapy may include, but is not limited to, IV fluids, antihistamines, and antipyretics. Increase monitoring of vital signs as medically indicated until the participant is deemed medically stable in the opinion of the Investigator.
 
If symptoms resolve following supportive treatment, the infusion may be restarted at 50% of the original infusion rate. Otherwise, dosing will be held until symptoms resolve and the participant should be premedicated for the next scheduled dose. If IRR occurs during titration (ie, at first or second dose), next dose should be administered at 50% of the original infusion rate.
 
Participants who develop Grade 2 toxicity despite adequate premedication and infusion rate reduction should be permanently discontinued from further trial treatment administration.
	Participant should be premedicated prior to next dose of study drug with antihistamine (eg, diphenhydramine 50 mg po) and antipyretic (eg, acetaminophen / paracetamol 500-1000 mg po).

**Table 10: Guidelines for Management of Acute Infusion-Related Reactions  
(Continued)**

CTCAE Toxicity Grade	Treatment	Premedication at Subsequent Dosing

Grades 3 or 4
 
Grade 3: Prolonged (eg, not rapidly responsive to symptomatic medication and/or interruption of infusion); recurrence of symptoms following initial improvement; hospitalization indicated for clinical sequelae
 
Grade 4: Life-threatening consequences; urgent intervention indicated
	
Stop infusion and increase monitoring of vital signs as medically indicated. Additional appropriate medical therapy may include, but is not limited to, IV fluids, IV steroids (eg, hydrocortisone 100-200 mg or corticosteroid equivalent), IV antihistamines, vasopressors, and antipyretics. Hospitalization may be indicated.
 
Participants with signs or symptoms that may be consistent with cardiac etiology should be assessed by ECGs, cardiac enzymes (eg, creatinine-MB isoenzyme, troponins, brain natriuretic peptide) to rule out myocardial infarction, and echocardiogram should be performed unless cardiac failure is ruled out by preceding investigations.
 
Participant is permanently discontinued from further trial treatment administration.
	
Any participant with a serious Grade 3 or any Grade 4 event will not be permitted to re-dose. Any subsequent redosing of nonserious Grade 3 events must be discussed and approved by the Medical Monitor.

CTCAE=Common Terminology Criteria for Adverse Events; ECG=electrocardiogram; IRR=infusion-related reaction; IRR=infusion-related reaction; IV=intravenous; MB=myocardial band; NSAIDs=non-steroidal anti-inflammatory drugs; po=orally.

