**Table 6: Adverse Event Grading Criteria**

Grade	Severity	Description
1	Mild	Asymptomatic or mild symptoms; clinical or diagnostic observations only; intervention not indicated
2	Moderate	Minimal, local, or noninvasive intervention indicated; limiting age-appropriate instrumental ADL a
3	Severe or medically significant but not immediately life-threatening	Hospitalization, or prolongation of hospitalization indicated; disabling, limiting self-care ADL b
4	Life-threatening consequences	Urgent intervention indicated
5	Death	Death related to AE

ADL=activities of daily living, AE=adverse event.

a Instrumental ADL refer to preparing meals, shopping for groceries or clothes, using the telephone, managing money, etc.

b Self-care ADL refer to bathing, dressing and undressing, feeding self, using the toilet, taking medications, and not bedridden.

Note that “severity” is a measure of intensity and that a severe AE is not necessarily an SAE.

Changes in the severity of an AE should be documented to allow assessments of the duration of the events at each level of intensity. AEs characterized as intermittent do not require documentation of onset and end date of each episode. When the intensity of an AE changes more than once a day, the maximum severity for the event should be recorded for that day. If the intensity changes over a number of days, these changes should be recorded separately (eg, as having distinct onset dates on one or more eCRF lines).

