## **7.10. Infusion Reactions**

Signs or symptoms of AEs during the infusion will be carefully monitored and treated according to standard of care. In addition, in the event of an infusion reaction, serum samples of PK and ADAs should be obtained, as well as a plasma sample for cytokine, etc. See [Section 14.3](#) for information on the management of infusion-related reactions.

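### Protocol Table 10 both ends study drug after every Grade 3 or 4 infusion reaction and allows redosing after a nonserious Grade 3 reaction, without saying which instruction governs

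*Protocol*

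**What the plan says.** Table 10 in Protocol Section 14.3 has three columns: the CTCAE grade, the treatment of the reaction, and premedication at subsequent dosing. Grades 3 and 4 share one row.

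- The Treatment cell of that row ends: "Participant is permanently discontinued from further trial treatment administration". It carries no exception and does not separate serious from nonserious events.
- The adjacent cell makes that separation. It first sets a bar: "Any participant with a serious Grade 3 or any Grade 4 event will not be permitted to re-dose". It then opens a route for the remaining events: "Any subsequent redosing of nonserious Grade 3 events must be discussed and approved by the Medical Monitor".

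The lead-in describes the table as giving "guidelines on management of acute infusion reactions as well as management of subsequent dosing instructions" and does not rank the columns. Section 7.10 only refers to Section 14.3 "for information on the management of infusion-related reactions". Sections 4.3.1 and 4.3.2 list general reasons for withdrawal and contain nothing specific to infusion reactions. The SAP has no rule on the point.

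**The concern.** A participant who has been permanently discontinued cannot be redosed, so the two cells cannot both be applied literally to a nonserious Grade 3 reaction.

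This is a participant-level safety rule in a multicountry, dose-blind study, and sites should get one answer from it. A site that follows the Treatment cell stops study drug and, under Protocol Section 4.3.1, ends the person's participation. A site that follows the adjacent cell asks the Medical Monitor whether dosing may continue.

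The difference would reach the data in two places. Adverse events leading to early drug discontinuation are a planned summary (SAP 7.4.3). Efficacy data later than 37 days after stopping drug are treated as missing under the main estimand (SAP 6.4.1.1).

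The former placebo participants receive AL002 for the first time in this study, and Protocol Section 1.3 names infusion-related reactions as a potential risk.

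**Working it through.** The plan gives no figure to reproduce. The check is a comparison of the text by case, followed by an illustration of scale.

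**Step 1: the two cells, case by case**

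| Reaction | Treatment cell | Adjacent cell | Agree? |
|---|---|---|---|
| Grade 4 | Stop permanently | No redosing | Yes |
| Serious Grade 3 | Stop permanently | No redosing | Yes |
| Nonserious Grade 3 | Stop permanently | Redosing possible if the Medical Monitor approves | No |

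**Step 2: can a nonserious Grade 3 reaction occur?** Yes. Table 10 gives three Grade 3 descriptors: a prolonged reaction, a recurrence after improvement, and an indication for hospitalization. The first two do not in themselves meet a seriousness criterion. The note under Table 6 in Section 7.5.1 says that "a severe AE is not necessarily an SAE". The redosing sentence itself presupposes such events.

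**Step 3: do the column roles settle it?** If the Treatment column dealt only with the acute episode and the last column only with later doses, the last column would govern. The Grade 2 row shows that this division does not hold, because its Treatment cell also sets next-dose rules: "Otherwise, dosing will be held until symptoms resolve and the participant should be premedicated for the next scheduled dose". The same cell states a condition when discontinuation is conditional: "Participants who develop Grade 2 toxicity despite adequate premedication and infusion rate reduction should be permanently discontinued". The Treatment cell for Grades 3 or 4 states none, so it can reasonably be read as absolute.

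**Step 4: does other text settle it?** No. Protocol Section 7.10 only points back to 14.3. Section 4.3.1 leaves withdrawal for a serious or intolerable event to the Investigator's opinion and says the Investigator may confer with the sponsor. Section 3.2.5 recommends consulting the Medical Monitor before removing a participant, but exempts discontinuations that the protocol mandates.

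**Step 5: scale**

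- N = 176 to 198 expected participants. SAP 3.5 derives this as 80% to 90% of 220: 0.80 × 220 = 176 and 0.90 × 220 = 198.
- r = proportion with a nonserious Grade 3 infusion reaction. The documents do not give it, so the values below are assumptions.
- Expected number = N × r. Chance of at least one = 1 − (1 − r)^N.

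| Assumed r | Expected, N = 176 | Expected, N = 198 | At least one, N = 176 | At least one, N = 198 |
|---|---|---|---|---|
| 0.1% | 0.18 | 0.20 | 16.1% | 18.0% |
| 0.5% | 0.88 | 0.99 | 58.6% | 62.9% |
| 2% | 3.52 | 3.96 | 97.1% | 98.2% |

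For example, at r = 0.005 and N = 176, the expected number is 176 × 0.005 = 0.88 and the chance of at least one is 1 − 0.995^176 = 0.586.

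**The case against.** The strongest reply is that the cells can be reconciled. The Treatment cell sets a default stop for a combined row, and the adjacent cell, in the only column headed for later dosing, carves out an exception for nonserious Grade 3. If the Treatment cell were absolute, both sentences beside it would have no function. This may well be what the authors meant. It is not written, however, and Step 3 shows why a careful site could read the row the other way.

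A second reply is that a site would probably telephone the Medical Monitor, as Section 3.2.5 recommends. Many would. But a site that takes the Treatment cell as binding falls under the exemption in that section and can withdraw the participant without the call that would resolve the question.

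A third reply is that little is at stake, and most of this stands:

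- Table 10 is presented as guidance on individual dosing and is not a study-level stopping rule.
- The stricter reading errs toward stopping drug, and neither reading exposes anyone to unsupervised redosing.
- Some Grade 3 reactions will be serious, and for those the cells agree.
- Applying one rate to everyone may overstate the count. Participants from the active arms have already had repeated infusions and completed the parent treatment period, and the newly exposed group starts at a lower dose with slow titration. Nothing in the documents supports the 2% scenario in particular.

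These points limit the size of the problem. They do not tell a site what to do after a nonserious Grade 3 reaction.

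**Conclusion.** The inconsistency is real and confined to nonserious Grade 3 infusion reactions, where one row of Table 10 gives two different instructions and nothing in the protocol or SAP ranks them. The consequence is that withdrawal from drug, and with it from the study, may differ between sites for the same event. The number affected is unknown and probably small: about 0.2 to 4 participants across assumed rates of 0.1% to 2%. No endpoint, analysis set or test is shown to be materially affected. The correction should be made because the rule concerns participant safety and costs almost nothing to put right.

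**What to change.** Replace the last sentence of the Treatment cell in the Grades 3 or 4 row with wording to this effect:

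> A serious Grade 3 reaction or any Grade 4 reaction ends study drug permanently. After a nonserious Grade 3 reaction, hold dosing; it may resume only once the Medical Monitor has discussed and approved the case. Without that approval, study drug is ended permanently.

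If the sponsor prefers the stricter rule, leave the Treatment cell as it is and delete the redosing sentence from the adjacent cell. Either choice removes the conflict, and which rule to adopt is a clinical decision for the sponsor.

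The cost is one sentence, by protocol clarification or in the next amendment, with no new procedures, visits or data.
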